### **3.0. SAMPLE ELIGIBILITY CRITERIA**

**Child/Parent Inclusion Criteria and Rationale:** Children and parents/caregivers will be eligible if: 1) the child is 3 – 8 years of age at time of enrollment (intervention content is not age-appropriate for other children); 2) patients with an expected treatment course of at least 3 days to receive moderate to high intensity chemotherapy and/or radiation therapy either in-patient or outpatient (children receiving chemotherapy are at risk for high symptom distress; 3-day treatment course is required to deliver study conditions and contributes to sample homogeneity); and 3) one parent/caregiver ( $\geq 18$  years of age) can be present for all sessions (study targets both child and parent/caregiver).

**Child/Parent Exclusion Criteria and Rationale:** Children and parents/caregivers will be excluded if: 1) the child and/or parent/caregiver do not speak English or 2) the child has a significant cognitive impairment that might hinder participation (determination made in consultation with attending physician, oncologist, and parents).

**Sample Size.** We will recruit a total sample size of 184 child and parent/caregiver dyads (368 total) and assume 15% attrition in order to retain 156 child and parent/caregiver dyads (78 dyads/group) at Time 3.

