**Data Collection & Randomization Procedures.** Following consent, the project manager will arrange a time for parents/caregivers to complete baseline (T1) measures during a routine clinic visit, prior to their next scheduled chemotherapy admission. A trained evaluator will administer measures in a quiet/private setting and remain available for questions. The child/parent or caregiver dyad will then be stratified by child age (preschoolers 3-5 years; school-agers 6-8 years) and randomized in blocks of six to the AME or attention control condition by our statistician. After the PI or project manager from the enrolling site receives randomization status from our study statistician, she will inform the parent/child of their randomization status and will then immediately schedule Session 1. Only the

project manager, PI, statistician, and intervener will know the child/parent dyad's randomization status. Evaluators will be blinded.

[figure not shown]
All study condition sessions will be video recorded to facilitate collection of child engagement and parent-child interaction data and monitor treatment fidelity. Sessions 1 and 2 are video recorded to desensitize children/parents to video recording; only Session 3 video data are analyzed for Aim 1. In our previous studies, video recording did not negatively affect participant accrual. An evaluator, blind to randomization status, will administer T2 measures after Session 3. Evaluators will administer T3 measures 30 days (+/- 7 days) post-intervention during a subsequent clinic visit or by telephone. Parent self-reports will be used to monitor use of study condition activities between sessions and between T2 and T3 data collections (Appendix 1).

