**Study Design.** This is a two-group, randomized, controlled trial. Children and one parent will be stratified and randomized in blocks of six to the AME intervention or attention control condition (see Study Schema). Child/parent dyads will be stratified by child age (preschoolers 3-5 yrs; school-agers 6-8 yrs). Both conditions are standardized and each group will receive three 45-minute sessions over 3 days. We chose a randomized, controlled trial over a single-group trial as a control group is optimal for ruling out confounding variables that may impact the relationships between the intervention, mediators, and outcomes. For example, a single-group trial requires a dose be measured to represent the intervention since the variable being mediated must have some variation. The dose may be impacted by several unknown factors that could make interpretation of results difficult. Our prior studies suggest that 1) a usual care condition would likely have high attrition and negatively affect study accrual, and 2) our audio-storybooks low dose condition was acceptable without behavioral benefits. Thus, we will use audio-storybooks as our attention control condition. The number of sessions and amount of contact time were selected based on average length of stay and findings from our preliminary studies which found immediate and longer-term (30 days post-intervention) benefit.

As in our preliminary studies, baseline data (Time 1) will be intervention intervention collected after consent. Time 2 data are collected post-Session 3. Parents/children are encouraged to use AME and low dose audio-storybooks activities between sessions and at home following discharge and self-reported frequency and duration of activities will be collected during sessions 2 and 3, and at T3 (30 days post-intervention). Data collection timelines are based on positive findings from our preliminary studies and inform our primary aims which examine mediation. Findings will inform a subsequent trial to examine long term benefits. See Study Schema for assessment timelines.

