## 7.0. STATISTICAL CONSIDERATIONS

As part of Preliminary Study 3, we have already created and successfully implemented a secure web-based system to capture the study data using the REDCap database management system, as well as a telephone log system and participant calendar that will enable the research coordinators to track and schedule participants' visits. We will review and process data using already-programmed multiple verification and edit-checking programs. We will also conduct rudimentary analyses to ensure that the data have been properly collected and to identify any outliers or errors.

Preliminary analyses: Prior to hypothesis testing, we will calculate coefficient alpha as a measure of internal consistency reliability on all multiple-item scales. Construct validity will be assessed by calculating Pearson or Spearman correlations between scales to determine if correlations are in the expected direction. We will assess multicollinearity between the scales for the mediators by examining the correlations above. If any pairwise correlations are 0.7 or higher we will not include both variables in a given model but fit separate models instead and acknowledge this issue in the interpretation. We will also compare the AME group to the attention control group with respect to demographic and baseline outcome variables using two-sample *t* tests, chi-square tests, or Fisher's

Exact tests as appropriate. We will control for any demographic variables that are not balanced in the models below (all models will adjust for baseline outcome). We will also control for site in all models.

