**Main analyses:** For analyses below we will analyze as randomized and attempt to collect outcome data on non-completers, following the intent-to-treat principle. For Aims 1 and 2, each outcome will be modeled separately. Also we will model T2 separately from T3. Thus, there will be a total of 12 models in Aim 1 (6 outcomes x two time points). In Aim 2, two outcomes will be examined and 3 potential moderators at two time points for a total of 12 (2 outcomes x 3 moderators x 2 time points) models. For Aim 1, our primary goal is to test mediation effects. Mediation effects will be estimated in an ANCOVA setting, fitting the appropriate mediation models using MPlus and then testing indirect effects using the percentile bootstrap approach to estimate the indirect effect. The multiple mediation model with three-path mediation effects specifies that the intervention will act through the proximal and distal mediator on the outcome and also have a direct effect on the outcome. Each outcome model will have 6 key predictors (intervention, two proximal mediators, 3 distal mediators), and control for T1, age (3-5 years vs. 6-8 years), site, and any imbalanced baseline covariates found above (allowing for up to 6 imbalances). Thus we will have up to 15 variables in any model. For Aim 2, we will test moderation effects by including the appropriate interaction terms of the potential moderator (dichotomized at the median) with the intervention indicator (AME vs. attention control) in our models. For all models in Aims 1 and 2, we will assess goodness-of-fit (GOF) using standard GOF measures (comparative fit index, root mean square error of approximation, and root mean square residual). For Aim 3, an exploratory aim, we will use ANCOVA to compare changes in child symptom distress at T2 and T3 between intervention and control groups. In light of positive findings, we next will explore models as in Aims 1 and 2 to assess for potential mediation and moderation effects for this outcome.

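### Randomisation is stratified by child age, but the exploratory Aim 3 ANCOVA as written omits the age stratum, so its test is mildly conservative if age is prognostic

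*Combined protocol and SAP*

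**What the plan says.** Section 5.0 (Study Design) states "Child/parent dyads will be stratified by child age", with levels 3-5 and 6-8 years, and Section 4.0 states that dyads are "randomized in blocks of six to the AME or attention control condition by our statistician".

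Section 7.0 sets covariates in two places:

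- **Preliminary analyses.** Every model adjusts for the baseline outcome, demographic variables that differ between arms are added, and "We will also control for site in all models". The age stratum is not in this list.
- **Main analyses.** The outcome model with six key predictors (arm, two proximal and three distal mediators) will "control for T1, age (3-5 years vs. 6-8 years), site" and imbalanced baseline covariates. Those predictors identify it as the Aim 1 mediation model. This is the only place where age is named as an adjustment covariate.

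For Aim 2, "we will test moderation effects by including the appropriate interaction terms of the potential moderator", split at the median, with the arm indicator. That sentence has no covariate list of its own. For Aim 3 the text is "we will use ANCOVA to compare changes in child symptom distress at T2 and T3 between intervention and control groups". If the result is positive, mediation and moderation models like those of Aims 1 and 2 follow.

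**The concern.** Permuted blocks within age strata hold the arms nearly equal on age, so age contributes almost nothing to the true sampling variability of the difference between arms. An analysis without age does not know this: it leaves the age-related variance in the residual and computes the standard error from it. To the extent that age predicts the outcome, the standard error overstates the true variability, the test rejects less often than its nominal level, and power is lost.

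The rule that adds imbalanced demographics will rarely repair this, because stratification is designed to prevent the imbalance that would trigger it.

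The analysis affected is the ANCOVA for Hypothesis 3.1, the direct comparison of arms on pain, fatigue and nausea at T2 and T3. Its result also decides whether the Aim 3 mediation and moderation models are explored, so a loss of power there carries forward.

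**Working it through.** **The plan's own figures.** Section 3.0 recruits 184 dyads to retain 156 after 15% attrition: 156 / 0.85 = 183.5, rounded up to 184. This reproduces. Section 7.0 allows up to 15 variables in a model: 6 key predictors + T1 + age + site + 6 imbalances = 15, with site counted once. This reproduces too, and it shows that the count comes from the mediation model, the one that names age.

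**Inputs.** From the documents: two age strata, blocks of six, 156 dyads retained (78 per group). Not in the documents: the correlation r between age stratum and symptom distress after adjustment for T1 and site; the significance level; the power. I assume r from 0.1 to 0.5, two-sided 5%, and 80% power with age included as a reference point.

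**Aim 3, closed form.**

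- Standard error without age relative to that with age: k = 1/√(1 − r²)
- True size of a nominal 5% test: 2 × [1 − Φ(1.96 × k)]
- Power where the model with age has 80%: Φ(1.96 + 0.84 − 1.96 × k)

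| r | k | True size | Power |
|---|---|---|---|
| 0.1 | 1.0050 | 4.89% | 79.72% |
| 0.2 | 1.0206 | 4.55% | 78.85% |
| 0.3 | 1.0483 | 3.99% | 77.25% |
| 0.5 | 1.1547 | 2.36% | 70.49% |

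For example, at r = 0.3, k = 1/√(1 − 0.09) = 1.0483.

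**Simulation check.** 6,000 null trials per setting, 156 dyads, blocks of six within two age strata, with a baseline covariate. The Aim 2 moderator is binary, with an assumed correlation of 0.2 with age. The ratio is mean model standard error over the empirical SD of the estimate; 1.00 means the standard error is right.

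| r | Aim 3 without age: ratio, rejection | Aim 3 with age: ratio, rejection | Aim 2 interaction without age: ratio, rejection |
|---|---|---|---|
| 0.1 | 1.002, 5.02% | 0.996, 5.05% | 1.004, 4.70% |
| 0.3 | 1.054, 3.62% | 1.005, 4.82% | 0.999, 4.87% |
| 0.5 | 1.154, 2.42% | 1.002, 5.13% | 1.011, 4.52% |

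For Aim 3 the simulation agrees with the closed form. It treats the 156 analysed dyads as fully balanced on age. Dropout after randomisation would loosen that balance a little and make the excess slightly smaller.

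**Aim 2.** Section 7.0 counts 12 models: 2 outcomes × 3 moderators × 2 time points. Prior distress (child or parent) is the moderator in 2 × 2 × 2 = 8 of them, and child age in the other 4. The quantity tested is the moderator-by-arm interaction. Stratifying by age does not balance age within moderator-by-arm cells, so age variance belongs in that standard error and the ratio stays at about 1.00. Adding age gains precision only: the mean standard error falls from 0.3382 to 0.3240 at r = 0.3, and from 0.3713 to 0.3240 at r = 0.5.

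**The case against.** Much of the case on the other side stands.

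- **Aim 2.** A reader might infer that the eight prior-distress models also omit age and that their standard errors are too large. The documents do not support this. The interaction terms are added to models whose covariates are not restated, and carrying over the covariates just listed for Aim 1, age included, is a natural reading. Even on the other reading, the interaction standard error is valid, as shown above.
- **Reach.** A reader might infer that the main results are at risk. They are not: the Aim 1 outcome models name age. What remains is one arm comparison at two time points, in an aim the plan calls exploratory. The Aim 3 follow-on mediation models are modelled on Aim 1 and so inherit age.
- **Direction.** The error is conservative. The treatment estimate is not biased and the type I error is not inflated.
- **Size.** Section 5.0 links younger age to higher distress but gives no magnitude, and it does not address physical symptoms after adjustment for baseline. T1 symptom scores are collected and may absorb much of any age effect. At r of 0.2 or less the excess is about 2% or less, costing about one point of power from 80%.
- **Remedy.** Adding the age stratum to every model without qualification would put two overlapping age splits into the four Aim 2 models where age is the moderator, or the same term twice if the median falls at the stratum boundary. The fix has to deal with this.

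None of this changes the fact that the Aim 3 ANCOVA, as written, omits the one factor by which the trial stratifies.

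**Conclusion.** The point holds for the Aim 3 comparison of arms. Age is a stratification factor, it is absent from the all-model covariate list, and the ANCOVA sentence does not name it. If age predicts symptom distress beyond T1 and site, the standard error is too large: by about 0.5%, 2% and 5% at r = 0.1, 0.2 and 0.3. The r = 0.5 row above is an upper bound for illustration. All these figures rest on assumed correlations, because the documents give none; if age has no residual association with the outcome, nothing is lost.

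For Aim 2 the defect is one of specification: the plan does not say clearly whether age is in the prior-distress models. If it is not, precision is lost but the tests remain valid. The consequence overall is small and conservative, and worth correcting because the correction is nearly free.

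**What to change.** In Section 7.0, Preliminary analyses, extend the sentence that puts site in every model so that it names two covariates for all models: site, and the age stratum used at randomisation (3-5 vs. 6-8 years). This covers the Aim 3 ANCOVA and settles the ambiguity in the Aim 2 prior-distress models.

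For the four Aim 2 models in which child age is the moderator, state that the moderator is the randomisation stratum (3-5 vs. 6-8 years) and not a separate median split, so that age enters once.

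The cost is the added wording and one degree of freedom per model that does not already contain the stratum. Age is already collected, and neither the sample size nor the visit schedule changes.
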